1. AMENDMENT HISTORY

Amendment No.	Protocol Version No.	Date issued	Author(s) of changes	Details of Changes made
1 (non-substantial)	1.1	18.05.22	[name]	Altering wording of post-nasal space biopsy to “a minimum of 6 weeks prior to nasal challenge (pages 15, 17 and appendix B) and added in section 15.4 to clarify epithelial cells will be cultured and stored within Cambridge.
2 (non-substantial)	1.2	04.07.22	[name]	Confirmed that only SARS-CoV-2 lateral flow (rather than PCR) is required prior to nasal sampling (as per University Department of Medicine Biological Safety Committee Review). Changed wording on pages 13, 16 and 35

2. SYNOPSIS

Title	Nasal Immune Challenge Study
Internal reference no	A095696
Design	Open label design using nasal challenge with a topical spray using saline or a Toll-like receptor (TLR)7/8 agonist and viral analogue (R848)
Participants	Healthy non-allergic volunteers Volunteers with allergic rhinitis with/without asthma
Sample Size	6 volunteers for sample collection to enable optimisation of protocols 24 for challenge (12 healthy and 12 allergic rhinitis with/without asthma)
Duration	2 years
Aims	
 1. To compare changes in gene expression at single-cell resolution in nasal mucosal samples and blood before and 24 hours after nasal TLR7/8 agonist (R848) challenge 2. To compare differences in nasal mucosal and blood single-cell gene expression between healthy and allergic participants 24 hours after R848 nasal challenge. 3. To assess systemic physiological measures and clinical tolerability of repeat R848 nasal challenge two weeks apart in healthy participants and those with allergic disease. 4. To measure change in levels of cytokines and chemokines in nasal mucosal lining fluid after repeat R848 nasal challenge. 5. To measure changes in peripheral immune (blood) responses to ex-vivo stimulation with lipopolysaccharide (LPS) before and after nasal challenge with R848.
Outcome Measures	
 1. Increase in CXCL10 nasal mucosal gene expression at 24 hours after nasal challenge with R848 compared to baseline. 2. Difference in CXCL10 nasal mucosal gene expression at 24 hours after R848 challenge between healthy subjects and those with allergic rhinitis. 3. Change in CXCL10 nasal mucosal protein in nasal mucosal lining fluid over 24 hours expressed as area under curve (AUC) between first and second nasal challenge with R848. 4. Change in participant's temperature between first and second nasal challenge with R848 (as a marker of clinical tolerability).
Eligibility	Adult males and females aged 18 years and above will need to meet inclusion and exclusion criteria. Participants in this study will be recruited from Cambridge University Hospital, University of Cambridge, volunteer databases and advertising in the Cambridge area.

3. ABBREVIATIONS

AE	Adverse event
AR	Allergic Rhinitis
ARwA	Allergic Rhinitis with Asthma
CUHFT	Cambridge University Hospital Foundation Trust
CI	Chief Investigator
CRA	Clinical Research Associate (Monitor)
CCRC	Cambridge Clinical Research Centre
CRF	Case Report Form
CRO	Contract Research Organisation
CT	Clinical Trials
EC	Ethics Committee (see REC)
GCP	Good Clinical Practice
GP	General Practitioner
ICF	Informed Consent Form
LPS	Lipopolysaccharide
NHS	National Health Service
NRES	National Research Ethics Service
PI	Principal Investigator
PIL/S	Participant/ Patient Information Leaflet/Sheet
PNIF	Peak Nasal Inspiratory Flow
R&D	NHS Trust R&D Department
REC	Research Ethics Committee
R848	Resiquimod
SAE	Serious Adverse Event
SAR	Serious Adverse Reaction
SOP	Standard Operating Procedure
SUSAR	Suspected Unexpected Serious Adverse Reactions
TMF	Trial Master File
TNSS	Total Nasal Symptom Score

4. BACKGROUND AND RATIONALE

Background

Acute respiratory viral infections cause significant morbidity, especially in vulnerable individuals and is a topic of immense significance during the current COVID-19 global pandemic. Respiratory diseases such as asthma and chronic obstructive pulmonary disease (COPD) involve inflammation of the airways and viruses are a major cause of exacerbations (1). Whilst new biological drugs targeting allergic and eosinophilic immune pathways have been developed for allergic asthma, therapeutic options for treating asthma exacerbations remain limited and rely on decades-old blunt tools such as oral corticosteroids. Development of new therapies and vaccines to combat viral respiratory tract infections is slow, partly because of the limited understanding of innate immune responses at the respiratory mucosal site of disease (2). Detailed characterization of such responses can facilitate biomarker definition for respiratory diseases, providing mechanistic insights and a platform for the testing of novel therapeutics.

Our understanding of the role of innate immunity to infection has recently undergone a paradigm shift as it is now recognized that innate cells (and not just adaptive immune cells) have the capacity to undergo “training” after infection via metabolic changes and epigenetic reprogramming (3). Pathogens can therefore modulate chromatin structure and the transcriptional programme of innate immune cells, which can result in altered but non-specific responses upon reinfection either with the same or heterologous stimuli. These epigenetic mechanisms may be particularly relevant in understanding how viral triggers (e.g. influenza) can lead to increased susceptibility to bacterial infections and cause pneumonia (e.g. due to *streptococcus spp.*) (4).

Most studies have focused on peripheral immune cells such as macrophages, but the concept of innate immune training has been extended to long-lived non-immune skin epithelial stem cells, which have the capacity for “inflammatory memory” (5). Allergic inflammatory memory has also recently been established in respiratory progenitor cells (6). Murine studies have highlighted the potential for structural cells (such as epithelial cells) to have the potential to mount immune responses (7). However, mechanisms of innate immune “memory” in human respiratory mucosal epithelial and immune cells in response to microbes and pathogen associated molecular patterns (PAMPs) are not well understood despite the respiratory tract being under a constant barrage of infectious stimuli.

Toll-like receptors (TLRs) play a critical role in the initial detection of microbes and PAMPs. TLR7/8 specifically detects RNA viruses such as influenza, rhinovirus, and coronavirus. Airway epithelial and immune cells express TLR7/8 and are therefore vital in mounting the innate immune response to viral infections, as well as helping shape adaptive immunity (8–10). Resiquimod (R848) is a single-stranded RNA viral analogue that binds to TLR7/8. When given systemically to treat human hepatitis C infection, it causes cytokine release and a flu-like syndrome (11). However, R848 has been successfully employed topically as a skin cream for actinic keratosis (12). TLR7 agonists have been developed for therapeutic use by repeated dose intranasal administration to target allergic inflammation in healthy volunteers and those with allergic rhinitis (13, 14).

Rationale for current study

Intranasal R848 administration has now been established in a human challenge model in healthy volunteers and in those with allergic rhinitis (AR) and allergic rhinitis with asthma (ARwA) by the chief investigator (15). In total, 44 volunteers have received intranasal R848 at a range of doses; 9 healthy volunteers received 10µg per nostril (n=9) with one person receiving 100µg per nostril (n=1); subsequently 35 volunteers received between 1-2µg per nostril based on weight (0.02µg/kg, healthy n=12, AR n=12, ARwA n=11). This dose was well

tolerated by all volunteers with minimal nasal symptoms and no significant change in airflow obstruction (FEV1) in volunteers with asthma. Intranasal R848 was well tolerated systemically with no change in physiological measures or serum inflammatory mediators compared to saline challenge. The study demonstrated that individuals with AR and ARwA have increased nasal mucosal interferon and chemokine responses compared to healthy volunteers. This is coupled with the observation that there is a small and transient reduction in peripheral eosinophil counts at 4 hours and in lymphocyte counts at 24 hours, a finding limited to volunteers with AR and ARwA. This suggests that leukocyte trafficking may be occurring from the peripheral blood to the nasal mucosa. These findings highlight that dysregulated mucosal innate immune responses are likely to be important in determining the clinical outcome of viral triggers.

R848 nasal challenge (up to 2µg per nostril) is therefore a practical, tolerable, and non-invasive method to stimulate and investigate TLR-driven respiratory mucosal innate immune responses in both health and disease.

Defining the cellular basis for TLR-driven innate immunity will help provide mechanistic insights into how these responses differ between individuals, its dysregulation in disease (such as during an asthma exacerbation) and susceptibility to secondary infections. Understanding the epigenetic mechanisms which regulate interferon and chemokine production may help identify the molecular drivers of excessive or dampened inflammation, helping to refine potential therapeutic targets. Given the current COVID-19 pandemic, the clinical translational model utilised in this study allows for a practical and straightforward method to assess the host factors which determine respiratory mucosal innate immunity.

The goal of this project is to utilize an established tolerable human nasal TLR agonist challenge model combined with single-cell transcriptomic and epigenetic techniques to precisely characterize innate immune responses and mechanisms of innate immune training in airway epithelial and immune cells. Samples will be collected from the nasal mucosa and blood before and after saline and R848 challenge. Cell cultures from airway epithelium and blood will also be established to assess the functional impact of R848 on cellular response to repeat stimulation with viral and bacterial ligands. Study populations will include healthy participants and those with allergic rhinitis with/without asthma in order to investigate how *in-vivo* innate immunity is altered in these populations. Some participants will also undergo repeat nasal challenge to assess mechanisms of innate immune memory in the respiratory tract.

5. OBJECTIVES

5.1 Primary Objectives

To compare changes in gene expression at single-cell resolution in nasal mucosal samples and blood before and 24 hours after nasal TLR7/8 agonist (R848) challenge

5.2 Secondary Objectives

To compare differences in nasal mucosal and blood single-cell gene expression between healthy and allergic participants 24 hours after R848 nasal challenge.

To assess systemic physiological measures and clinical tolerability of repeat R848 nasal challenge two weeks apart in healthy participants and those with allergic disease.

To measure change in levels of cytokines and chemokines in nasal mucosal lining fluid after repeat R848 nasal challenge.

To measure changes in peripheral immune (blood) responses to ex-vivo stimulation with lipopolysaccharide (LPS) before and after nasal challenge with R848.

5.3 Exploratory Objectives

To establish cell culture models from primary nasal epithelium and immune cells to understand the functional impact of R848 on cellular responses to repeat stimulation with viral and bacterial ligands.

6. STUDY DESIGN

6.1 Summary of Trial Design

The first stage of the study will include up to 6 participants (healthy or allergic disease) to undergo nasal mucosal tissue and blood collection without any nasal challenge. These samples will be used to optimise the protocols required for downstream processing, e.g. for single cell and epigenetic analysis.

The main component of the study is an open label design employing nasal challenge with a topical spray using saline or a TLR7/8 agonist R848. The aim is to perform deep immunophenotyping of nasal mucosal tissue and peripheral blood before and after nasal challenge with R848 and compare responses between non-allergic and allergic individuals. Some participants will undergo repeat challenge two weeks later with assessment of cytokine, chemokine, and gene expression profiles to determine which cells contribute to innate immune memory of previous exposures and how this may be altered in disease.

After an initial screening visit to determine eligibility, participants constituting equal numbers of non-allergic and allergic individuals will undergo nasal challenge with R848 (n=24). They will have sampling performed for up to 24 hours and can choose to go home or stay overnight in the Cambridge Clinical Research Centre (CCRC). This will be the end of the study for half of the participants.

The remaining half will be invited to subsequently undergo repeat saline (n=2) or R848 (n=10) challenge approximately two weeks later to determine clinical tolerability, assess for exaggerated or dampened nasal mucosal immune responses and investigate mechanisms of innate immune memory, and how they may differ between the groups.

The maximum duration for participants in the study are as follows (Appendix A):

Single challenge study (n=12): one day

Double challenge study (n=12): two days spread two weeks apart

6.2 Primary Outcome Measure

1. Increase in CXCL10 nasal mucosal gene expression at 24 hours after nasal challenge with R848 compared to baseline

Secondary Outcome Measures

1. Difference in CXCL10 nasal mucosal gene expression at 24 hours after R848 challenge between healthy subjects and those with allergic rhinitis
2. Change in participant's temperature between first and second nasal challenge with R848 (as a marker of clinical tolerability)
3. Difference in CXCL10 nasal mucosal protein in nasal mucosal lining fluid over 24 hours expressed as area under curve (AUC) between first and second nasal challenge with R848.

Exploratory Outcome Measures

1. Difference in CXCL10 after ex-vivo stimulation of blood samples with LPS before and 24 hours after nasal challenge with R848
2. Single-cell gene expression and epigenetic profiles in mucosal tissue and blood before and after nasal challenge with R848
3. Comparison of single-cell and epigenetic profiles between healthy and allergic disease groups

7. TRIAL PARTICIPANTS

7.1 Overall Description of Trial Participants

Adults will be considered for inclusion in this study. They will either be healthy individuals with no history of allergy, or they will have a history of allergic rhinitis (hay fever) with/without physician diagnosis of asthma.

For the sample optimisation phase of the study (n=6), volunteers will only be required to provide nasal mucosal tissue (using curettage and or brush) and a blood sample and will therefore not undergo a detailed medical screening visit.

For participants undergoing nasal challenge, they will be recruited within the parameters of the following criteria:

7.2 Inclusion Criteria

- Participant is willing and able to give informed consent for participation in the study.
- Male or female aged 18 years and above
- Able (in the Investigators opinion) and willing to comply with all study requirements.
- Willing to allow his or her General Practitioner and consultant, if appropriate, to be notified of participation in the study.
- Female participants of child-bearing potential and male participants whose partner is of child-bearing potential must be willing to ensure that they or their partner use effective contraception during the study
- Participant has clinically acceptable laboratory and ECG at enrolment.
- Negative lateral flow or polymerase chain reaction (PCR) test for SARS-CoV-2
- For healthy volunteers:
 - No clinical history of allergic rhinitis, asthma or eczema
 - Negative skin prick tests or specific IgE response to a panel of common aeroallergens: cat, dog, grass pollen, tree pollen, house dust mite, fungal spores
 - Normal blood eosinophil count (< 300 cells/ μ L)
 - Normal baseline forced expiratory volume (FEV₁) i.e. \geq 80%
- For volunteers with allergic rhinitis with or without asthma:
 - A clinical history of allergic rhinitis symptoms (sneezing, runny or itchy nose) in response to aeroallergens
 - At least one positive skin-prick test or specific IgE response to a panel of common aeroallergens: cat, dog, grass pollen, tree pollen, house dust mite, fungal spores
 - Pre-bronchodilator FEV₁ \geq 50% predicted
 - Participants are permitted to have physician-diagnosed mild to moderate asthma which is not poorly controlled as evidenced by an Asthma Control Questionnaire (ACQ-5) score of \leq 1.5.
 - If they have asthma, they are permitted to be on inhaled corticosteroid (ICS) and a long-acting beta agonist (LABA), but no other controller medication.
- Have had no other courses of medication including nasal and systemic corticosteroids, whether prescribed or over-the-counter, in the four weeks before first study dose other than mild analgesia, vitamins and mineral supplements or, for females, oral contraceptives.

7.3 Exclusion Criteria

- Recent infections in past 14 days before screening: especially upper respiratory tract illnesses (including colds and influenza), sore throats, sinusitis, infective conjunctivitis.
- Lower respiratory tract infection in past 28 days
- Nasal anatomical defects, precluding use of nasal sampling techniques
- The participant may not enter the study if any of the following apply:
 - Female participants who are pregnant, lactating or planning pregnancy during the study.
 - Respiratory diseases (other than hay fever or asthma where specified)
 - Significant medical history of hepatic, cardiovascular, gastrointestinal, renal, endocrine, infective, haematological, autoimmune, metabolic, rheumatological, neurological, dermatological or neoplastic conditions
 - Extreme obesity (BMI >40)
 - Depression and psychiatric disorders
- Any other significant disease or disorder which, in the opinion of the Investigator, may either put the participants at risk because of participation in the study, or may influence the result of the study, or the participant's ability to participate in the study.
- Participants who have participated in another research study involving an investigational product in the past 12 weeks
- Smoking in previous 6 months

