8. STUDY PROCEDURES

Pictures of the study procedures are outlined in appendix A and an outline of study procedures in relation to study visits is outlined in appendix B.

Nasal lavage: 10ml of normal saline will be administered and collected gently through a disposable plastic olive-shaped device into both nostrils prior to each challenge. This acts to “clean” the nasal mucosa of nasal debris prior to challenge and the nasal washing will be discarded.

Nasosorption: Nasal mucosal lining fluid will be collected non-invasively using nasosorption initially regularly (0min, 15min, 30min, 1h, 2h) then at two-hourly intervals (4h, 6h, 8h, 24h) after each challenge to assess the kinetics of interferon, cytokine and chemokine production.

Nasal mucosal epithelium: Nasal mucosal epithelial cells will be collected at the screening visit, baseline (0h) and 24 hours after each challenge to assess transcriptional and epigenetic signatures and to culture epithelial cells in the lab. Therefore, a maximum of up to three sets of samples per volunteer will be taken from half of the group undergoing single challenge (n=12), whilst the remainder of the group undergoing double challenge will have a total of five sets of samples taken (n=12). Up to five sets of nasal curettage samples were taken per volunteer in a prior study using R848 with good tolerability and no withdrawal of participants from the study¹⁵. Topical anaesthetic spray may be offered prior to procedures.

- **Nasal brushings** are taken using a small cytology brush from the nasal inferior turbinate – up to two samples will be taken (one from each nostril).
- **Nasal curettage** involves the use of a small plastic curette to gently “scrape” a small amount of tissue from the nasal inferior turbinate – up to four samples will be taken (two from each nostril).

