Post-nasal space biopsy will be an optional procedure in order to obtain a small sample of tissue (0.5cm) taken from the postnasal space using endoscope and forceps under topical local anaesthetic. It will be performed by a trained Ear, Nose and Throat (ENT) surgeon ([name]) in a specific area of Addenbrookes hospital with dedicated facilities for the procedure. The purpose of this is to obtain a larger and deeper volume of tissue than the nasal curettage/brushings to facilitate detailed molecular phenotyping particularly of immune cell subsets, which are found underneath the epithelial layer. The procedure is generally well tolerated, and complications are rare. This procedure is more invasive than performing nasal curettage/brushings and will therefore only be performed twice in up to 12 people. These participants will only undergo a single nasal challenge and not the second repeat challenge. Volunteers who agree to have the procedure will have the first sample collected at the screening visit. There will then be a minimum of 6-weeks (to ensure wound healing) before performing nasal challenge with saline (up to n=2) or R848 (up to n=10), and a subsequent post-nasal space biopsy performed 24 hours after challenge.

Blood: Blood will be collected on the following occasions:

- Screening visit for routine safety and eligibility (9ml) and DNA analysis (8.5ml)
- Before (0h) and after (24h) each nasal challenge for single cell analysis and Truculture (13ml each time-point)
- Before (0h) and twice after (4h, 24h) nasal challenge for serum and full blood count (9ml each time point).

This means that half of the volunteers undergoing single challenge (n=12) will provide a total of approximately 70ml blood over three visits and the remaining half undergoing 2 challenges (n=12) will provide a total of approximately 125ml blood over five visits.

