8.5 Discontinuation/Withdrawal of Participants from Study Treatment

Each participant has the right to withdraw from the study at any time. In addition, the investigator may discontinue a participant from the study at any time if the investigator considers it necessary for any reason including:

- Ineligibility (either arising during the study or retrospective having been overlooked at screening)
- Significant protocol deviation
- Significant non-compliance with treatment regimen or study requirements
- An adverse event which requires discontinuation of the study or results in inability to continue to comply with study procedures
- Consent withdrawn

The reason for withdrawal will be recorded in the CRF. If the participant is withdrawn due to an adverse event, the investigator will arrange for follow-up visits or telephone calls until the adverse event has resolved or stabilised.

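### The 14-day infection exclusion is counted back from screening, so it covers none of the 14 days before challenge for biopsy volunteers (up to 12) and essentially none before the 12 second challenges

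*Combined protocol and SAP*

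**What the plan says.** Section 7.3 ties the 14-day infection exclusion to screening: "Recent infections in past 14 days before screening: especially upper respiratory tract illnesses (including colds and influenza". The next bullet, "Lower respiratory tract infection in past 28 days", names no visit from which the 28 days run. Section 8.2 requires freedom from possible COVID symptoms for 14 days before enrolment, which is also not a challenge date. The medication criterion in section 7.2, by contrast, is tied to dosing: "in the four weeks before first study dose".

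The challenges come later than screening. For biopsy volunteers, whose first biopsy is taken at the screening visit, section 8 says: "There will then be a minimum of 6-weeks (to ensure wound healing) before performing nasal challenge". Section 6.1 plans, for the half who continue, "repeat saline (n=2) or R848 (n=10) challenge approximately two weeks later". No screening-to-Visit-1 interval is given for volunteers without biopsy.

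Checks nearer to challenge are:
- a negative SARS-CoV-2 test, a short medical assessment and symptom scores at Visits 1 and 3 (section 8.3, Appendix B);
- CRF recording of every adverse event, related or not, with onset and end dates (sections 10.1.1 and 10.2);
- the medication washout before first dose (section 7.2);
- mucosal tissue at 0h before each challenge (section 8, Appendix B);
- the investigator's option to discontinue for reasons that include "Ineligibility (either arising during the study or retrospective having been overlooked at screening" (section 8.5).

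**The concern.** The sponsor evidently regards a recent respiratory infection as a reason not to enter a volunteer. As dated, the criterion has lapsed before many of the challenges it would be expected to protect.

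This matters because R848 is an RNA-virus analogue. Section 4 says its receptors detect influenza, rhinovirus and coronavirus. A natural cold shortly before challenge is therefore an exposure of the same kind as the one under study, and could move nasal CXCL10. The direction is not known: section 6.1 plans to "assess for exaggerated or dampened nasal mucosal immune responses" after prior exposure.

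The outcome most open to this is the CXCL10 AUC comparison between first and second R848 challenge (sections 6.2 and 11.1). It rests on 10 pairs, and no baseline subtraction is stated. A cold caught between the two challenges would be mixed with the effect of the first challenge.

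**Working it through.** **1. Date overlap.** Take screening as day 0; the exclusion covers days −14 to 0. For a challenge D days after screening, the number of the 14 preceding days that are covered is max(0, 14 − D).

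- Biopsy volunteers (section 8): D ≥ 6 × 7 = 42, so cover is 0 of 14. The window before challenge opens on day 42 − 14 = 28 or later, leaving at least 28 days between the two windows.
- Second challenges (section 6.1): D = g + i, where g is the screening-to-Visit-1 gap and i the interval between challenges. At i = 14, cover is 0 for every g ≥ 0. At g = 0, intervals of 13, 12 and 10 days give 1, 2 and 4 days. At g = 1 these become 0, 1 and 3.
- Other first challenges: cover is 14 − g (7 days at g = 7, 0 at g ≥ 14), and g is not stated.

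There are 24 first and 12 second challenges, 36 in all. If all 12 biopsy places are filled, 12 + 12 = 24 of 36 (67%) have no cover at the nominal two-week interval.

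**2. How many challenges would follow a cold.** The documents give no rate, so 1, 2.5 and 4 colds per person-year are assumed. The probability that a cold starts in the preceding 14 days is p = 1 − exp(−rate × 14/365).

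| Rate per year | p | 12p | 10p | At least one of 10: 1 − (1 − p)^10 |
|---|---|---|---|---|
| 1 | 3.8% | 0.5 | 0.4 | 32% |
| 2.5 | 9.1% | 1.1 | 0.9 | 62% |
| 4 | 14.2% | 1.7 | 1.4 | 78% |

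The 12p column applies to the 12 second challenges and, separately, to the biopsy volunteers' first challenges if all 12 places are filled. The 10p column is for second R848 challenges. The last column is not the chance that a result changes. No credit is taken for existing checks.

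**3. Effect on the repeat-challenge comparison.** Section 11.1 names a paired Wilcoxon signed-rank test. Assumptions: 10 complete R848 pairs, normal paired differences with SD 1, a true increase of 1 SD, each pair affected with probability p, and a shift of 1 or 2 SD of the paired difference. The test uses the exact two-sided cut-off (attained level 4.9%), with 200,000 simulated trials per setting. Power without shifts is about 78%.

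Power in % (1 SD shift / 2 SD shift):

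| Pattern of shifts | 1 per year | 2.5 per year | 4 per year |
|---|---|---|---|
| Random direction | 77 / 74 | 75 / 67 | 73 / 61 |
| Upward, cold equally likely before either challenge | 76 / 69 | 72 / 59 | 70 / 52 |
| All downward, second challenge only | 74 / 66 | 67 / 51 | 61 / 39 |

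Two-sided type I error stays at about 5% in the first two patterns. It reaches 5-8% only if every shift goes one way at the second challenge.

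**The case against.** The strongest reply is that the trial already has several layers of protection. An active cold at Visit 1 or 3 would often show in the assessment or symptom scores. A cold between visits is an adverse event, so section 10.2 already requires its dates on the CRF. The washout in section 7.2 would catch many medicated colds before a first challenge. The 0h tissue measures CXCL10 expression directly before each challenge, which partly protects the within-person primary outcome. All of this stands. What is left is narrower: adverse-event recording depends on observation or spontaneous report, and nothing asks about a cold that has already resolved.

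The reply also limits the size. Biopsy volunteers have no second challenge, so their gap cannot touch the repeat-challenge AUC, and its effect on first-challenge outcomes has not been quantified. The cold rate, shift sizes and true effect are all assumed. The pattern with colds before either challenge gives section 7.3 no credit at first challenges, where cover is in fact unknown.

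Three stronger readings are tempting, and the documents do not support them:
- A reader might infer that sections 7.2 and 7.3 contradict each other. They do not: infection and medication criteria may have different reference dates.
- A reader might infer that intercurrent infections would go unrecorded. Section 10.2 covers them, though without a prompt.
- A reader might take the 39% power figure, or inflated false positives, as the expected result. The 39% combines the highest rate, the larger shift and every shift downward; inflation needs every shift in one direction. Nothing in the documents establishes a direction.

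**Conclusion.** The point holds as a date calculation from the protocol's own text. The infection window gives no cover before challenge for up to 12 biopsy volunteers and essentially none before the 12 second challenges, and no other provision restores an infection-free period. A stated criterion that lapses before up to two thirds of challenges is more than missing detail.

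The consequence is modest and falls mainly on one secondary outcome. In the random-direction, 1 SD case the loss is 1 to 5 percentage points of power, with no change in type I error. Larger losses need larger or one-directional shifts. The trial's validity is not in question. Priority is low to moderate, and confidence in the size is limited by the outside assumptions.

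**What to change.** - **Reconcile the dates.** The sponsor should reconcile the reference date of the 14-day and 28-day criteria in section 7.3 with the challenge timings in sections 6.1, 8 and 8.3. This review does not say when a challenge may proceed.
- **Prompt and record.** Before each challenge, ask about respiratory infection since the last visit, as a supplement to adverse-event recording. Word the question to separate infection from rhinitis, since half the participants have allergic symptoms. Record the actual interval between challenges.
- **Pre-state a sensitivity analysis.** Repeat the CXCL10 analyses omitting challenges preceded by a recorded infection, with that term defined in advance. Under the same 1 SD assumption, power is about 68% with 9 pairs and 61% with 8. It should therefore support the main analysis and not replace it.
- **Use the pre-challenge samples.** Check 0h tissue and 0-minute nasosorption for raised CXCL10. Section 8 describes collection "using nasosorption initially regularly (0min, 15min, 30min, 1h, 2h" and onwards, but the nasosorption row of Appendix B starts at 15 minutes. Reconcile the two, and state whether the 0-minute sample precedes lavage.

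The cost is minor wording, one CRF question and one extra analysis. Some first challenges may need rebooking if the reference date moves.
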